2.2. Study Duration and Study Sites

The ACCSIS – Chicago UH3 Implementation Phase will last for four years (November 2019 to October 2023). In the UH3 Implementation Phase, we will have 4 clusters of clinics from four different FQHCs. Each cluster will have 5 to 12 clinics and a total of 20 to 35 primary care providers (internist, family practice physician, nurse practitioners, and physician assistants). Table 1 summarizes the characteristics of our FQHC partners. Together, our

Table 1: Characteristic of Partner Health Care Systems

	Total Patients	% of Racial Minority	% at or below 200% poverty	% of Uninsured	CRC Screening Rate	Adjusted Quartile Ranking on CRC Screening ¹	No. of Clinics ²	No. of Providers
PCC Community Wellness Center	48,357	92.2%	93.1%	9.3%	30.0%	Quartile 4	11	60
Aunt Martha's Youth Service Center, Inc.	51,343	80.9%	96.2%	16.5%	32.9%	Quartile 3	12	21
Lawndale Christian Health Center	51,235	96.9%	97.6%	30.2%	35.0%	Quartile 2	5	35
Near North Health Service Corporation	37,102	94.6%	97.3%	35.1%	31.0%	Quartile 3	7	20

1. Adjusted Quartile Ranking provides a health center's adjusted quartile ranking compared to health centers nationally for each of the clinical performance measures. Clinical performance for each measure is ranked from quartile 1 (highest 25% of reporting health center) to quartile 4 (lowest 25% of reporting health centers).

2. Reported by partner health care system.

partner FQHCs served 188,037 patients in 2016, and at least 10% of these patients were ≥ 50 years old. It is important to point out that three of our partners' CRC screening rates were in the lower third and fourth quartiles compared to other FQHCs in the nation, indicating room for improvement. We will continue to monitor their ranking throughout the study.

[figure not shown]
3. STUDY DESIGN AND PROCEDURES

3.1 Study Design

We will use a stepped wedge cluster randomized trial design to assess the effectiveness of our proposed multilevel intervention. Although it will be preferable to use a traditional cluster-randomized trial to test our multicomponent, multilevel intervention, we will need a larger number of clusters, which will be more expensive and infeasible. Also, it is unacceptable for our partner(s) assigned to a control group to not benefit from well-studied evidence-based interventions. Since the stepped wedge design retains some elements of randomization and has the advantage for multiple data collection points over a long period and allows clusters to act as their own control, it is the best alternative to the gold standard.

In the UH3 Implementation phase, we will partner with four FQHCs. We will randomize the four FQHCs to either group 1 or group 2. The biostatistician will conduct the randomization independently from the research team. The difference between the two groups is that group 2 will start the implementation later. We will implement our multilevel intervention in three phases. In phase 1, we will implement the provider education and community outreach component. In phase 2, we will add the mobile patient reminder and the provider assessment and feedback components. In phase 3, we will add the CRC patient navigation component. Figure 1 shows our stepped wedge study design.

Figure 1: Stepped Wedge Study Design.

3.2 Study Intervention

CRC screening and follow-up processes are complex and include several steps and interfaces. However, very few interventional studies have simultaneously targeted patient-, provider-, and organization-level factors. At the patient-level, factors influencing motivation and willingness to undergo CRC screening or diagnostic evaluation after a positive result may include negative beliefs or attitudes about cancer screening, lack of health insurance coverage, suboptimal knowledge about the necessity of screening and/or follow-up diagnostic evaluation, and other SES barriers [13-20]. At the provider-level, factors include overburden [21],

communication issues [22], lack of a place for referrals [23], and decisions made by the provider not to screen or follow-up [24]. At the organization-level, factors include interruption or breakdowns in the workflow, nonadherence to organizational policy, and lack of “intra-organizational” and “inter-organizational” coordination [25]. Interventions that simultaneously focus on reducing barriers across several levels will likely be more effective on increasing rates of CRC screening, follow-up, and referral-to-care. In this study, we will partner with the Quality Improvement Department at each partner FQHC to implement provider education, provider assessment and feedback, and mobile patient reminder as part of the organizational CRC Screening Quality Improvement Initiative.

3.2.1 Provider-Level Component:

Provider Education CRC screening, follow-up and surveillance guidelines, cultural competency and communication training for primary care providers is a must if we are to increase CRC screening and follow-up adherence and decrease cancer disparities among racial/ethnic and low-income populations, as well as in the general population. Drs. [name] and [name] are well-known CRC control experts and will identify critical messages on CRC screening guidelines and options, and provide in-person educational training to providers in our partner FQHCs. In addition, they will conduct refresher sessions and yearly training. [name] and [name] will also train a healthcare member of the ACCSIS-Chicago team to serve as a practice facilitator, who will have a medical background and understands the clinical practice, to provide one-on-one training for new providers and providers whose CRC screening rates fall below the benchmark on two consecutive provider assessment and feedback reports. The facilitating sessions for providers whose CRC screening rates below the benchmark will be limited to 10-15 minutes to refresh key messages on CRC screening and to identify possible barriers. In our experience, underperformers were often the result of failure to adequately document FIT results into the EMR system rather than an unwillingness to screen patients. Tracking these potential barriers can significantly improve screening rates.

Provider Assessment and Feedback Provider assessment and feedback is designed to both evaluate provider performance in recommending and offering screenings to age-eligible patients (assessment) and present providers with information about their performance in providing CRC screening services (feedback). We will work with the quality improvement team at our partner sites to generate clinic- and provider-specific reports on CRC screening completion rate, referral rate, as well as follow-up for abnormal results and referral to oncology care. Also, we will monitor group performance (e.g., the mean performance for a specific site or group). Providers will receive a quarterly report that allows providers to compare their performance to that of their peers and to learn from each other's successes. Our research team will deliver the reports in person for the first two quarters to provide support and open discussion to address any concerns about the process and the interpretation of the results. Education and training will be provided to reinforce compliance when a partner site's group or individual performance is at or below baseline on two consecutive reports.

3.2.2 Organization-level Component

Patient Text Message Reminder Completion of screening and follow-up evaluation involves patient compliance with the provider recommendation. It is critical not only to remind providers to order the screening test but also remind patients to complete the test. We will work with our partner sites to implement a mobile patient reminder as part of the quality improvement initiative. The patient reminder app combines technologies in mobile communication and artificial intelligence to engage patients and deliver customized messages and timely information to empower patients to complete their screening. Text message reminder has been reported to have a positive impact on patient compliance. [25-26]

CRC Patient Navigation Completion of screening and follow-up evaluation involves patient compliance with the provider recommendation. Therefore, we will add a CRC navigator to facilitate patient compliance at both organization and patient levels. Patient navigation is a healthcare delivery support strategy and was first introduced by Harold P/ Freeman in 1990 as a way to reduce cancer disparities by eliminating barriers to timely care between the point of suspicious finding and the resolution of the finding by diagnosis and treatment [27]. Most patient navigation programs have been created to improve rates of CRC screening [28-36], and few studies have used patient navigators to improve outcomes related to diagnostic follow-up after a positive test result [37-41].

Our partner FQHCs will hire a patient navigator for their CRC Patient Navigation Program with support from the research team. All hired patient navigators will participate in a 2-day training session. Our patient navigator training includes didactic and clinical training sessions, as well as CITI human subject training. Training will take place 3 months before the implementation of the component with ongoing training every quarter through the duration of the program. Drs. [name] and [name] and the research team will lead the training. The training will focus on, but not limited to, the following topics: CRC and CRC screening methods, the follow-up process after a positive FOBT/FIT, cancer treatment, navigator roles and responsibilities, common patient barriers, communication skills with health care providers and other professionals, cultural competency, local community resources, and the oral consent process and the participant's right. Furthermore, the CRC navigators will have the opportunity to spend time in the University of Chicago endoscopy suite with [name] and the oncology clinic with [name] observing colonoscopies and patient-provider interactions. The goal of these activities is to create an interactive environment that allows navigators to gain knowledge through direct experience. CRC navigators will undergo pre and post-training evaluation to assess their knowledge for CRC screening and follow-up care. All CRC navigators will meet with a research team member biweekly to discuss their cases, share information, and address any issues associated with their roles and responsibilities.

ILColonCARES Program Many safety net settings with low resources offer FOBT/FIT as the initial screening option for their patients [42, 43]. However, providers in these settings often face an ethical dilemma: whether to offer no screening or to offer the screening knowing that the patient with a positive FOBT/FIT result cannot obtain timely follow-up colonoscopy services. In Chicago, the lack of specialty services for colonoscopy access within our safety net system is a significant problem with the average wait of 18 months to complete a diagnostic colonoscopy. This alone can significantly contribute to disparities in colorectal cancer mortality with studies showing that a one year delay in follow up for a positive FIT can result in a twofold increase in colorectal cancer risk [44]. Thus, it is important to increase the ability of safety net providers to access high quality and timely colonoscopies for their underinsured or uninsured patients when a follow-up is needed. ILColonCARES Program is a HIPAA compliant web-based portal designed and developed using a user experience approach to link non-networked healthcare systems. Some hospital health systems in Chicago have committed to providing no-cost colonoscopy services to uninsured FIT positive individuals. The ILColonCARES Program overcomes many barriers to receipt of colonoscopy services across systems: 1) access to care for uninsured patients, 2) point of service scheduling, 3) bidirectional communication. The ILColonCARES Portal was created by a CDC funded program and is housed in the University of Chicago. Our partner FQHCs will have access to the portal.

3.2.3 Community-Level Component

Community Outreach Reliance solely on primary-care settings to promote and provide colorectal cancer screenings can only reach those who have regular contact with the health-care system. In ACCSIS-Chicago, we will partner with the National Outreach Network program at the University of Chicago Comprehensive Cancer Center to conduct community outreach activities. We will expand the current community outreach networks and will build new partnerships with high-risk communities located near our partner FQHCs. We will continue the NCI's Screen to Save (S2S) Initiative through small media campaigns in the high-risk communities and conduct community education events. For participants without a regular place for care, we will work with our partner FQHCs to develop a referral channel for them to obtain CRC screening.

3.3 Recruitment For Patient Navigation

We will have recruitment posters and flyers in each exam room and patient waiting area at our partner sites. Patients who have a CRC screening order and need help to complete the screening, such as making an appointment for the colonoscopy at a local hospital or instruction on the preparation for the colonoscopy, can call the patient navigator at each partner site directly. Patient navigators help patients with any challenges that may inhibit screening completion by discussing the process through a series of up to 4 phone calls. Participation in the patient navigation program is voluntary.

3.4 Inclusion And Exclusion Criteria

The inclusion criteria for the patient navigation component include 1) having an order for CRC screening, and 2) capable of giving consent. We will not exclude any participants who meet the inclusion criteria based on age, gender, language, or racial or ethnic group.

3.5 Data Sources

During the first three months, we will work with the Quality Improvement Department at each partner site to collect baseline data on primary outcomes through the existing electronic medical record or chart reviews. After we start implementing the multilevel intervention, we will collect primary outcome data each quarter until the completion of the 4-year study period. Table 2 summarizes the primary outcome measures.

Table 2. Outcome Measures for the Multilevel Intervention

Outcome	Operational Definition	Data Sources	Data Collection Period	Level of Data Analysis
Patient CRC screening rates	Numerator: # of patients completed CRC screening Denominator: # of patients eligible for CRC screening	• EMR • Chart reviews as needed	Every quarter	Level 2, Level 3, Level 4
CRC ordering rates	Numerator: # of patients received order for CRC screening Denominator: # of patient eligible for CRC screening	• EMR • Chart reviews as needed	Every quarter	Level 2, Level 3, Level 4
Patient notification rates (FOBT/FIT +)	Numerator: # of patients notified Denominator: # of patients had FOBT/FIT +	• EMR • Chart review as needed	Every quarter	Level 2, Level 3, Level 4
Time to notification of positive results	# of days between notifying a patient with a positive result and the result available to the provider	• EMR • Chart reviews as needed	Every quarter	Level 2, Level 3, Level 4
Follow-up diagnostic evaluation referral rates	Numerator: # of patients received referral for evaluation Denominator: # of patients had FOBT/FIT +	• EMR • Chart reviews as needed	Every quarter	Level 2, Level 3, Level 4
Time to referral for follow-up diagnostic evaluation	# of days between the referral and the result available to the provider	• EMR • Chart reviews as needed	Every quarter	Level 2, Level 3, Level 4
Follow-up diagnostic evaluation completion rates	Numerator: # of patients completed diagnostic evaluation as ordered Denominator: # of diagnostic evaluation referral made	• EMR • Chart reviews as needed	Every quarter	Level 2, Level 3, Level 4
Time to completed diagnostic evaluation	# of days between the positive FOBT/FIT result available to the provider and the completion of the diagnostic evaluation	• EMR • Chart reviews as needed	Every quarter	Level 2, Level 3, Level 4

* Level 2 = Provider level; Level 3 = Clinic level; and Level 4 = organization level.

For the CRC navigation component, we will collect data from the navigator activity logs, including the number of patients using the service, length of the encounter, types of encounter (e.g., transportation arrangement or making an appointment), and types of action taken. We will also ask patients who received navigation services to complete a 10-item patient satisfaction survey adapted from the patient satisfaction survey developed by the NCI-sponsored Patient Navigation Research Program, which has been validated through rigorous structural and reliability analysis [45]. For the community outreach, we will collect annual data on the number of education events conducted and the number of community members educated.

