The multilevel intervention components will include 1) provider education, 2) provider assessment and feedback, 3) patient reminder using mobile platform, 4) patient navigation, and 5) community outreach. The first three components will be implemented as part of the quality improvement project at the partner FQHCs. During the first six months, we will collect baseline data at our partner FQHCs. After we start implementing the multilevel intervention, we will collect outcome data every three months until the completion of the 4-year study period. At the clinic and provider levels, we will work with the Quality Improvement Department to collect outcome data on 1) CRC screening rates, 2) CRC screening order rates, 3) CRC screening completion rates, 4) follow-up diagnostic evaluation rates, 5) follow-up diagnostic evaluation completion rates, and 5) time to completion of diagnostic evaluation. At the patient level, we will collect data on patient navigation service utilization and the satisfaction of the services.

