4. DATA ANALYSES

In order to evaluate the effect of the multilevel, multicomponent intervention, we will take a step-by-step approach. First, each intervention effect at each time phase will be estimated separately using linear-mixed effects models. The estimate of intervention effect in each model will be used to test if additional intervention component significantly affects outcome measures. Next, we will develop a grand model including all three intervention effects simultaneously in addition to the models described above.

In this study, patients are nested within providers and providers are nested within clinics. The problem with nested data structures is that they violate the independence assumption of traditional regression models. Thus, we will use multilevel modeling to analyze our data. We will start with the unconditional three-level random intercept models:

$$\text{Level - 1: } Y_{ijk} = \beta_{0jk} + \epsilon_{ijk};$$

$$\text{Level - 2: } Y_{ijk} = \beta_{0k} + u_{jk} + \epsilon_{ijk}$$

$$\text{Level - 3: } Y_{ijk} = \beta_0 + v_k + u_{jk} + \epsilon_{ijk}$$

where Y_{ijk} is the observed outcome for patient i with provider j in clinic k . β_0 is the mean response across all clinic. v_k is the random effect of clinic k , u_{jk} is the random effect of provider j , and ϵ_{ijk} is the residual error. The random effects and residual errors are assumed independent of one another.

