Adding predictor variables to the models is straightforward. For example, the level-3 random intercept and slope model with one predictor measured at each level is $Y_{ijk} = \beta_0 + \beta_1 X_{1ijk} + \beta_2 X_{2jk} + \beta_3 k + v_k + u_{jk} + \epsilon_{ijk}$, where $\beta_0 + \beta_1 X_{1ijk} + \beta_2 X_{2jk} + \beta_3 k$ is the fixed effect of the model and $v_k + u_{jk} + \epsilon_{ijk}$ is the random effect of the model. The fixed effect of the model specifies the overall mean relationship between the response and the predictor variables. The random effect of the model specifies how the provider and clinic specific relationships differ from the overall mean relationship. To assess the potential mediator effect, we will use the causal variable and the mediator variable as predictors in the model. To assess the cross-level interaction effects, we will add a product term to the model. For example, the model for a level-1 predictor (e.g. age) cross-level and interact with a level-2 predictor: $Y_{ijk} = \beta_0 + \beta_1 X_{1ijk} + \beta_2 X_{2jk} + \beta_3 (X_{1ijk} \bullet X_{2jk}) + u_{0jk} + u_{1jk} X_{1ijk} + \epsilon_{ijk}$. Since one of the patient-level (level-1) outcome measures is dichotomous (whether the patient adherence to follow-up diagnostic evaluation after a positive result within 9 months or not), we will add another level-1 model for the binary data:

$$\text{Level - 1: } \log [P_{ijk} / (1 - P_{ijk})] = \beta_{0jk} + \beta_1 X_{1jk}.$$

In this study, we will use the restricted maximum likelihood (**REML**) to estimate variances. REML treats the regression coefficients as unknown quantities to be estimated based on sample data and subtracts the needed degree of freedom when computing variance estimates. Since REML only allows for tests of models that differ in their variances, we will calculate the intraclass correlation (**ICC**) to access the variation in response variable across providers and across clinics prior to testing the models. At the end of the analysis, we will use the likelihood ratio test to

compare the nested models. The deviance values ($-2 \log L$) for the two models can be used to decide which model better fits the data:

$$(-2 \log L_{\text{Reduced Model}}) - (-2 \log L_{\text{Full Model}}) = \text{deviance}_{\text{Reduced Model}} - \text{deviance}_{\text{Full Model}}$$

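### Table 2 counts follow-up completion per referral made with no time window, while Section 4 names a 9-month outcome per positive patient that Table 2 omits; the two need reconciling

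*Combined protocol and SAP*

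**What the plan says.** Section 3.5 presents Table 2 as the summary of the primary outcome measures. The table has eight rows, five rates and three durations, all collected quarterly and analysed at provider, clinic and organization level.

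- Its only follow-up completion rate is "Numerator: # of patients completed diagnostic evaluation as ordered Denominator: # of diagnostic evaluation referral made". No window is given, nor any rule for the quarter to which a completion belongs.
- The referral rate is "Numerator: # of patients received referral for evaluation Denominator: # of patients had FOBT/FIT"-positive. The notification rate has the same denominator.
- The time-to-completion row runs from the positive result being available to the completed evaluation. It does not say how patients who never complete are handled.

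Section 4 describes one of the patient-level outcomes as dichotomous: "whether the patient adherence to follow-up diagnostic evaluation after a positive result within 9 months or not". It adds a logit model for this outcome. The 9-month window appears nowhere else. The summary lists "4) follow-up diagnostic evaluation rates, 5) follow-up diagnostic evaluation completion rates" and defines neither.

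Section 4 also says that the phase-specific effect estimates will be "used to test if additional intervention component significantly affects outcome measures". As background to the ILColonCARES Program, Section 3.2.2 cites an "average wait of 18 months to complete a diagnostic colonoscopy" in the Chicago safety net.

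**The concern.** The trial aims to raise follow-up of positive results, and the natural quantity for that aim is the share of positive patients who are evaluated. The completion row conditions on referral, a step that the trial counts as an outcome in its own right. If an intervention phase brings in more referrals, and these complete no more often than earlier ones, completion per referral does not rise although more positive patients are evaluated.

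The missing window is a separate problem. With long waits, an open-ended completion rate depends on how much time has passed since referral. In a stepped wedge, later referrals come mostly from intervention periods, so observation time is linked to phase. A phase comparison could then partly reflect the counting rule.

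The plan holds the material for a better measure in Section 4, but does not say how that outcome relates to the Table 2 row or which of them carries the conclusion.

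**Working it through.** The documents give no sample size, power, effect size or expected follow-up rate, so there is no figure to reproduce. The check compares definitions and then illustrates the consequences. Every rate below is assumed. The only sourced figure is the 18-month wait; a 6-month mean is shown as a shorter assumed case.

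**Definitions.** Of the eight Table 2 rows:

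- rates with FOBT/FIT-positive patients as denominator: 2 (notification, referral);
- completion rates per positive patient: 0;
- rows with a completion window: 0;
- rows containing the 9-month outcome: 0.

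**Units.** The completion row divides patients by referrals. With 60 completers among 100 referred patients, one referral each gives 60/100 = 60%; 1.25 referrals each gives 60/125 = 48%.

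**Denominator.** Let referral rise from 60% to 80% of positives. Earlier referrals complete at 60%, added ones at rate c.

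- Before: per positive 0.60 × 0.60 = 36%; per referral 60%.
- After: per positive = 0.36 + 0.20c; per referral = (0.36 + 0.20c)/0.80.

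| c | per positive | per referral |
|---|---|---|
| 20% | 40% | 50% |
| 40% | 44% | 55% |
| 60% | 48% | 60% |
| 75% | 51% | 64% |

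Completion per positive rises in every line. Completion per referral falls, stays flat or rises according to c.

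**No window, one common cut-off.** Suppose 60% of referrals eventually complete in every phase, so nothing truly changes. Waits are exponential with mean m months, and referrals are spread evenly and observed for a to b months by a count at month 48. The completed share is 0.60 × [1 − (m/(b − a)) × (e^(−a/m) − e^(−b/m))].

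| mean wait | referrals from first 6 months (a = 42, b = 48) | referrals from last 12 months (a = 0, b = 12) |
|---|---|---|
| 18 months | 55% | 16% |
| 6 months | 60% | 34% |

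With gamma waits (shape 2, computed numerically) the pairs are 58% and 10%, and 60% and 32%.

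**No window, completions over referrals in the same quarter.** Referrals step from 60 to 80 per 100 positives per quarter, and 60% still complete eventually. The earlier 60 referrals per quarter yield a steady 36 completions. The added 20 yield, in quarter q, 0.60 × (20/3) × [G(3q) − G(3q − 3)], where G(T) = T − m(1 − e^(−T/m)). The rate is (36 + that number)/80.

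- m = 18: quarter 1 is (36 + 0.95)/80 = 46%; quarter 4 is (36 + 5.30)/80 = 52%; quarter 8 is (36 + 8.56)/80 = 56%.
- m = 6: quarter 1 is (36 + 2.56)/80 = 48%; quarter 4 is (36 + 9.89)/80 = 57%.

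The rate starts at 60% and returns towards it, while eventual completion per positive goes from 36% to 48%.

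**The 9-month outcome on the same inputs.** Ignoring the delay from result to referral, the share of referrals completed by 9 months is 0.60 × (1 − e^(−9/m)): 23.6% for m = 18 and 46.6% for m = 6. Completion per positive within 9 months then moves from 0.60 × 0.236 = 14% to 0.80 × 0.236 = 19%, or from 28% to 37%.

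**The case against.** The strongest reply is that Section 4 already plans the missing outcome. Table 2 lists only levels 2 to 4, so a level-1 outcome may sit outside it by design. This stands in part: a reader might infer that the plan has no outcome per positive patient, and Section 4 shows otherwise. What remains is that the outcome is absent from the table of primary measures and nothing ties the two together.

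Second, completion per referral is a defensible measure. Section 3.2.2 bases the text reminder and navigation on patients complying with the provider's recommendation, and completion given referral measures that step. The referral row would show a referral gain. This stands, and is why the row should be kept. Multiplying the two rates does not fully replace a direct measure: it needs one referral per patient and the same cohort in both, and the plan states neither.

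Third, the illustrations are built on assumptions. The 18-month wait is a background figure, given where the protocol discusses access for underinsured and uninsured patients; the partner FQHCs have 9.3% to 35.1% uninsured. A single count at month 48 fits poorly with quarterly collection, and the same-quarter dip is transient. All of this stands and limits the claim about size.

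Three further inferences are not supported:

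- That the binary model is unusable because its upper levels are not written out. Section 4 adds only a new level-1 equation, so the provider and clinic effects given just before it plausibly carry over.
- That provider education and feedback are expressly aimed at diagnostic referral. The education text speaks of "increase CRC screening and follow-up adherence", and the feedback text of "reports on CRC screening completion rate, referral rate, as well as follow-up for abnormal results", where the referral meant may be for screening. The clear support is Table 2's own referral row.
- That the 9-month measure would show a larger effect. On the 18-month inputs it moves 5 points, against 12 for eventual completion.

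**Conclusion.** The point holds as a mismatch of definitions with consequences for interpretation. The primary completion row has no window, mixes patients with referrals, and conditions on a step that is itself an outcome; Section 4's 9-month outcome is not in the table. Read alone, the row can stay flat or fall while more positive patients are evaluated, and without a window it can mix phase with observation time.

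A reader might infer that the trial will report no effect or harm where there is benefit. The documents do not support that. It would require the row to be read without the referral row, and it depends on how added referrals complete, on real waits and on the counting rule, none of which the documents give. The textual facts are certain; the size of any distortion is unknown. The change should be made, because it is cheap and uses the plan's own window.

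**What to change.** Add a row to Table 2 and align Section 4 with it: the proportion of FOBT/FIT-positive patients, one record each, who complete diagnostic evaluation within 9 months of the result being available to the provider. Section 4 speaks of adherence and does not fix the start of the clock, so both sections should adopt the same definition. Assign each patient to a phase by result date, and analyse with the Section 4 logit and that section's provider and clinic random effects. State that conclusions about follow-up of positives rest on this measure.

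Keep completion per referral as a step measure of compliance with the referral, counted per referred patient in the same cohort and with a fixed window. Define or delete the undefined follow-up evaluation rate in the summary.

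The core change is wording: positive results and the time from result to completion are already to be collected. The plan should state these downsides:

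- Results with less than 9 months before the last extract are immature. If that extract is at study end (assumed), this is 9/48 = 19% of calendar time.
- Windows cross phases, mainly diluting the baseline contrast. If phase 1 follows baseline directly in the first group (assumed; Figure 1 is not shown), the average share of a baseline patient's window falling after baseline is 1 − (6/2)/9 = 67% for the 6-month baseline of Section 2.1, or 1 − (3/2)/9 = 83% for the 3 months of Section 3.5. A sensitivity analysis that censors incomplete follow-up and treats phase as a time-varying exposure is a useful check; it adds some analysis work.
- The outcome measures timely completion, not ever completing.

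Optional additions are an extract of positives dated at least 9 months before phase 1, and a description of the positive group by phase.
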